7. STUDY DESIGN

Please see Appendix A for study flow diagram.

This is a prospective randomised controlled study designed to assess the impact of specific training interventions on surgical trainee's operative performance and patient outcomes following primary elective THR. We will also study the performance and patient outcomes of both 'Experts' and 'Fellows' in an additional comparator group, which will allow a potential expert standard in THR to be defined.

All study participants will be recruited from 2 Hospitals within the Thames Valley (Oxford) Post-graduate Medical Deanery, and will be composed of: Trauma & Orthopaedic Specialty Registrars ('StRs') holding national training numbers; Consultant Orthopaedic Surgeons ('Experts'); and Orthopaedic Arthroplasty Fellows ('Fellows'). Over the 18-24 month anticipated study period we aim on recruiting a total of up to 16 StR's, 8 Fellows, and 5 Experts. See section 9 for further details on participant recruitment.

StR's will be randomised in a 1:1 ratio to receive either: routine normal Deanery training (the control group, n=8); or routine normal Deanery training with additional simulation-based and cognitive learning (the intervention group, n=8). The intervention group will receive this training for 1-2 hours per week over a 4 to 6-week period. The 'Experts' and 'Fellows' will not be eligible for any intervention, and will act as a separate comparator group.

All participants will be assessed intra-operatively at set timepoints when performing elective primary THR surgery on patients within the named NHS Hospitals. The timepoints will vary depending upon each group. Each StR enrolled into this study will be assessed at a minimum of 8 separate THR operations over a 6-month period, commencing at 6 weeks in to their 6-month clinical placement. Both the 'Fellows' and 'Experts' will be assessed at a minimum of 5 separate THR operations depending upon the reliability of their performance data.

All patients in this study will have been listed for routine elective primary THR surgery under a named Orthopaedic Consultant on the NHS. There will be no interventions or deviations from routine clinical practise regarding the pre-operative investigations or work-up, the operation itself, the peri-operative care, or post-discharge follow-up.

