8. PARTICIPANT & PATIENT IDENTIFICATION

8.1. Consultants, Fellows, and Specialty Registrars

Group 1 ('StR's'): Trauma & Orthopaedic Specialty Registrars on Arthroplasty clinical placements.

Group 2 ('Experts' and 'Fellows'): Consultant Orthopaedic Surgeons, and nationally appointed Orthopaedic Arthroplasty Fellows.

Inclusion Criteria

Group 1 ('StR's'): All Specialty Registrars holding a National Training Numbers (NTN) in Trauma & Orthopaedic Surgery within the Thames Valley (Oxford) Deanery and who are or will be working on arthroplasty clinical placements at either the NOC, Oxford University Hospitals NHS Foundation Trust, or WGH, Buckinghamshire Healthcare NHS Trust over the specified recruitment period will be eligible for participation in this study. We anticipate recruiting 2 StR's from each recruitment centre every 6 months, over an 18 to 24-month period (total n = 12-16).

Group 2 ('Experts' and 'Fellows'): All Consultant Orthopaedic Surgeons with a sub-specialty practise in adult reconstructive (arthroplasty) surgery holding substantive posts at the NOC are eligible for participation in this study. The Consultant Orthopaedic Surgeons at WGH will not be required for the intra-operative assessment within this study, as we will gather sufficient motion data from the NOC Consultants to be able to benchmark an 'expert' performance. Nationally appointed Orthopaedic AF's working at either at either the NOC, Oxford University Hospitals NHS Foundation Trust, or WGH, Buckinghamshire Healthcare NHS Trust over the specified recruitment period will be eligible for participation in this study. We anticipate recruiting 2 AF's every 6-months over an 18 to 24-month period (total n = 6-8)

Exclusion Criteria

- Inability to comply with study procedures or timetable

- Moving outside of the area, relinquishing their position, or National Training Number.

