9.2. Informed Consent

The PI ([name]), or a suitably qualified deputy, will take informed consent from every participant involved in this study. This will be taken at their visit before any study specific procedures are performed.

Each participant must personally sign and date the latest approved version of the Informed Consent form at this visit. Written and verbal versions of the PIS and Informed Consent form (ICF) will be presented to the participants detailing no less than: the exact nature of the study; what it will involve for the participant; the implications and constraints of the protocol; and any risks involved in taking part. It will be clearly stated that the participant is free to withdraw from the study at any time for any reason, and with no obligation to give the reason for withdrawal. The participant will be allowed as much time as wished to consider the information, and the opportunity to question the Investigator, or other independent parties in order to decide whether they will participate in the study. Written Informed Consent will then be obtained by means of participant dated signature and dated signature of the person who presented and obtained the Informed Consent. A copy of the signed Informed Consent will be offered to the participant. The original signed form will be retained by the PI ([name]) at the study site

Visit 1 - Group 1 ('StR's):

Following enrolment for participation in this study, the StR's will be randomly allocated to receive either routine normal Deanery training (the 'control' group), or routine normal Deanery training plus additional simulation training (the 'intervention' group). Following randomisation all StR participants will undergo a baseline written and practical skills assessment within the OOSEC.

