9.5 Blinding and code-breaking

Standard surgical practise will be followed. Patients are not formally blinded to which Surgeon (Consultant, Fellow, or StR) performs their operation, and are informed if requested. In line with standard surgical practise and training within the NHS, patients will provide informed consent that they understand no guarantees can be given that a particular person will perform the procedure. The person will, however, have appropriate experience.

Due to the nature of this study the StR's cannot be blinded to their allocations into either the 'control' or 'intervention' groups, however the assessment methods and any assessors will be blinded.

9.6 Description of study intervention(s),

The intervention to be tested is the simulation-based and cognitive learning package, which will be delivered to a randomised sub-group of 50% of the StR's recruited into this study. This will be delivered in a supervised setting within the OOSEC over a 4-week period for between 1 to 2 hours per week, over 3 to 4 consecutive but separate six-month placements (please see Appendix A for Study Flow Diagram). This will take place on a Wednesday afternoon, which is when all the Regional StR's are due to attend teaching in Oxford at the NOC.

The OOSEC is a secure enclosed laboratory space within the NOC, which contains all the necessary equipment required to run the simulation-based and cognitive learning training. The simulation training in general may include:

- 1) Focussed workshops on saw-bone models (simulated bones)
- 2) Digital and computer-based cognitive learning packages
- 3) Virtual reality platforms.

All participants within group 1 (StR's) will be asked to attend and complete baseline and final assessments within the OOSEC, which will consist of a multiple-choice questionnaire (MCQ) and a simulated procedure. Participants within group 2 (Consultants and Fellows) will only be required to complete a baseline simulated procedure.

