11 STATISTICS AND ANALYSIS

Analysis of motion data.

Motion data from the wireless sensors produces performance surrogate markers such as: the number of movements (major & minor); total path length; and smoothness/economy of movement. Data distributions will be assessed for normality using the Shapiro-Wilk test. Previous studies show such data are not normally distributed, and we would expect to use non-parametric tests, such as the Mann-Whitney U test to compare the performance metrics between the 2 groups of participants (StR's against Experts & Fellows). The Mann-Whitney U test will also be used to compare performance metrics between the two sub-groups of StR's (control and intervention), and also within the intervention sub-group in order to compare performance before and after training.

Performance metrics within all groups of participants will be reported using descriptive statistics to outline the central tendency (mean, median, and mode) and variation (range, variance, and standard deviation) in readings obtained. The Kruskal-Wallis one-way analysis of variance (ANOVA) test will be used to test for differences in the mean values obtained for all performance metrics between the two groups of participants. The Wilcoxon signed-rank test will be used to determine any differences in performance metric between the two groups.

Analysis of other routinely obtained data

X-ray (radiograph) analysis:

X-rays will be reviewed by two independent Consultant Orthopaedic Surgeons who will be blinded to the patient and lead surgeon's identity in order to reduce bias. There are several important parameters to be evaluated when reviewing a pelvic x-ray, therefore we will ask each reviewer to allocate a categorical global rating (see below) for both the pre- and post-operative x-rays. [5] The Chi-squared test will be used

to determine if there are any significant differences between each group, and also intra-group differences (for example StR's before and after additional training).

Pre-operative x-ray

- 1: Hip osteoarthritis without significant bone loss.
- 2a: Hip osteoarthritis with significant bone loss on acetabular side.
- 2b: Hip osteoarthritis with significant bone loss on femoral side.
- 3: Hip osteoarthritis with significant bone loss on both acetabular and femoral sides.

Post-operative x-ray

- 1: Excellent implant position and restoration of hip anatomy.
- 2a): Good overall with minor imperfections on acetabular side.

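### The arm comparison of registrars' operative metrics leaves out the OOSEC baseline score; adding it as one pre-specified covariate would probably gain precision at little cost, by an amount the documents do not fix

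*Combined protocol and SAP*

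**What the plan says.** **Test.** On the motion metrics, section 11 states: "The Mann-Whitney U test will also be used to compare performance metrics between the two sub-groups of StR's (control and intervention". The reason given is distributional: "Previous studies show such data are not normally distributed, and we would expect to use non-parametric tests". No covariate, regression, ANCOVA or between-arm change analysis appears in section 11. Its only before-and-after comparisons between training stages are within groups of registrars, not between the arms.

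**Baseline.** Section 9.2 (Visit 1) states: "Following randomisation all StR participants will undergo a baseline written and practical skills assessment within the OOSEC". Section 9.6 describes "baseline and final assessments within the OOSEC, which will consist of a multiple-choice questionnaire (MCQ) and a simulated procedure". Both arms sit it.

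**Operative outcomes.** Trainee outcome measures begin once simulation training is complete (section 2), and theatre assessments start 6 weeks into the placement (section 7). The in-theatre metrics therefore have no pre-training value. The OOSEC baseline is the only pre-training measure of registrar skill that the protocol collects.

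**Size and allocation.** Section 7: "StR's will be randomised in a 1:1 ratio to receive either: routine normal Deanery training (the control group, n=8", with the same number in the intervention group. Section 9.4 gives 6 to 8 per arm, allocated by sealed envelope, and aims only for an even spread over the two hospitals. Eligibility (section 8.1) covers "All Specialty Registrars holding a National Training Numbers (NTN) in Trauma & Orthopaedic Surgery within the Thames Valley (Oxford) Deanery" on the relevant placements, with no limit by training year.

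**The concern.** The registrar is the randomised unit and there are few of them. Starting skill may vary widely, because eligibility is not limited by training year. The protocol's own rationale (section 5) is that the sensors can tell surgeons of different training levels apart, so some link between starting skill and the operative metrics is plausible. Neither the allocation nor the analysis takes account of it.

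If the link exists, an unadjusted test treats predictable variation between registrars as noise. The interval is then wider than it need be, and a real effect of simulation training is more likely to be missed. The measure that could reduce this is already being collected in both arms.

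**Working it through.** **Inputs from the documents.** 8 registrars per arm (section 7), or 6 to 8 (section 9.4); Mann-Whitney test without covariate (section 11); baseline in both arms (sections 9.2 and 9.6). The documents give no power calculation for the registrars, so there is no planned figure to reproduce.

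**Assumptions.** Two-sided alpha 0.05; one summary value per registrar; normal scores; no dropout; effects in units of the SD of the per-registrar summary; correlation rho between baseline score and summary, varied from 0 to 0.7.

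**Step 1: chance imbalance.** In SD units, the difference between arms in mean baseline skill has standard error sqrt(2/n).
- n = 8: sqrt(2/8) = 0.50. P(|difference| > 0.5 SD) = 2[1 - Φ(0.5/0.50)] = 2[1 - Φ(1.00)] = 32%.
- n = 6: sqrt(2/6) = 0.577. P = 2[1 - Φ(0.5/0.577)] = 2[1 - Φ(0.866)] = 39%.
- An imbalance of 0.5 SD moves the unadjusted difference by rho × 0.5, which is 0.25 SD at rho 0.5.

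**Step 2: precision.** The unadjusted difference in means has standard error sqrt(2/n). With one covariate it is, on average, about sqrt(2/n) × sqrt[(1 - rho²)(1 + 1/(2n - 4))]. The last factor is the price of estimating the slope. At n = 8 it is 1 + 1/12 = 13/12, so the standard error goes from 0.50 to:
- rho 0: 0.50 × sqrt(1.00 × 13/12) = 0.52
- rho 0.3: 0.50 × sqrt(0.91 × 13/12) = 0.50
- rho 0.5: 0.50 × sqrt(0.75 × 13/12) = 0.45
- rho 0.7: 0.50 × sqrt(0.51 × 13/12) = 0.37

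Against an unadjusted comparison of means, break-even is where (1 - rho²) × 13/12 = 1, so rho = sqrt(1/13) = 0.28.

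**Step 3: power by simulation.** Model: y = rho·x + sqrt(1 - rho²)·e + d·arm, with x and e standard normal and 100,000 trials per setting. Three tests were compared: exact Mann-Whitney, ANCOVA (2n - 3 = 13 df), and Quade's test (rank both variables, regress one on the other, compare the residuals between arms). Results at 8 v 8 and d = 1.0:

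| rho | Mann-Whitney | ANCOVA | Quade | ANCOVA gain (points) | Quade gain (points) |
|---|---|---|---|---|---|
| 0 | 44% | 43% | 42% | about -1 | about -2 |
| 0.3 | 44% | 46% | 45% | +2 to +3 | 0 to +1 |
| 0.5 | 44% | 54% | 50% | about +10 | about +6 |
| 0.7 | 44% | 70 to 71% | 63 to 64% | +26 to +27 | +19 to +20 |

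Not all of the ANCOVA gain comes from the covariate. An unadjusted t-test has 46% power under the same normal model, so about 2 of the 10 points at rho 0.5 come from leaving ranks and about 8 from adjustment.

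**Step 4: other settings.**
- 8 v 8, d = 0.5: Mann-Whitney about 15%; ANCOVA gains about 1, 3 and 9 points at rho 0.3, 0.5 and 0.7.
- 8 v 8, d = 1.5: Mann-Whitney 77%; ANCOVA 76%, 80%, 87% and 96% at rho 0, 0.3, 0.5 and 0.7; Quade 74%, 77%, 83% and 92%.
- 6 v 6, d = 1.5, rho 0.5: Mann-Whitney 59%, ANCOVA 72%, Quade 67%. Part of this gap arises because the exact Mann-Whitney test has a true size of only 4.1% at 6 v 6.

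**Step 5: type I error.** With d = 0, every method rejects in 4.0% to 5.5% of trials at either sample size.

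**The case against.** **The gain may be small.** The baseline is a written test and a simulated procedure. The outcome is sensor data from supervised live surgery on varying patients, with a Consultant who may adjust or take over (section 9.7). Noise in the outcome lowers the correlation further. With an assumed intraclass correlation of 0.2, the mean of 8 operations has reliability 8 × 0.2/(1 + 7 × 0.2) = 0.67, so a correlation of 0.5 with true operative skill is seen as 0.5 × sqrt(0.67) = 0.41. Nothing in the documents supports 0.5 as a central value. At 0.3 ANCOVA gains 3 points or less, and Quade's test, the closer replacement for data expected to be non-normal, gains almost nothing. This stands, and it is why the size is given only as a range.

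**The covariate is measured after allocation.** Section 9.2 places the baseline after randomisation, and section 9.5 says registrars cannot be blinded. Effort at baseline could differ by arm, and adjusting for such a score could add bias. The order of sections 9.2 and 9.3 suggests that training comes later, but the text does not say so outright. This stands and sets a condition on the fix.

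**The score is undefined.** No section says how the simulated procedure is scored, and it is absent from the outcomes in section 6. This stands; the score has to be named.

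**The unit of analysis is not stated.** The powers above assume one value per registrar. If 8 operations each were pooled as independent, clustering would be the larger problem: at an assumed intraclass correlation of 0.3 the design effect is 1 + 7 × 0.3 = 3.1, and type I error is 2[1 - Φ(1.96/sqrt(3.1))], about 27%. That is a separate point, but the fix must settle the unit.

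**The planned test is valid.** A reader might infer that a lucky draw of stronger registrars would be mistaken for a training effect more often than the stated error rate allows. It would not. On per-registrar summaries, chance imbalance is already reflected in the randomised p-value.

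**Conclusion.** The point holds as one of efficiency. The planned comparison of operative metrics omits the only pre-training skill measure, which both arms already provide. In a trial of 6 to 8 per arm this leaves avoidable noise in the estimate if that measure predicts theatre performance.

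The size depends on the correlation. Under the assumptions listed, at 8 v 8 and a 1.0 SD effect, the change in power runs from about -1 point (rho 0) to +26 to +27 points (rho 0.7) for ANCOVA, and from about -2 to +19 to +20 for Quade's test.

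Three stronger readings go beyond the documents:
- A definite loss of 5 to 10 points. For ANCOVA at 8 v 8, that needs rho of about 0.4 to 0.5 and an effect of 0.8 SD or more, neither of which is stated.
- A biased or invalid analysis. Type I error stays near 5%.
- Adjustment as a rescue for the sample size. Power for a 1.0 SD effect stays below 80% even at rho 0.7.

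**What to change.** In section 11:
- Make the primary control-versus-intervention comparison of each operative metric an ANCOVA on one summary per registrar, for example the mean of the log metric over the assessed operations. A log-scale mean also goes some way to meet the stated worry about non-normality.
- Use the OOSEC baseline simulated-procedure score as the single covariate. Name the score and how it is derived before data are seen. Do not add the written test, as only 13 degrees of freedom are available at 8 v 8.
- Report the adjusted difference with a 95% confidence interval. If a rank-based test is preferred, use Quade's test for the p-value only, since it does not itself supply that interval.
- Keep the unadjusted Mann-Whitney test, on the same per-registrar summaries, as a sensitivity analysis.

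In section 9.2, state that the baseline is completed before any simulation training and, at no extra cost, before the envelope is opened. If that order cannot be assured, treat the adjusted result as supportive only.

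**Cost.** Wording changes, and a decision on how the simulated procedure is scored. No new visits are needed, and no new data provided the score is recorded. If the baseline proves uninformative, the price is one degree of freedom: about 1 point of power at 8 v 8 for ANCOVA and about 2 to 4 for Quade's test.

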The outcome measures will be surgeon-specific and patient-specific. These outcome measures for the 'Trainee' group will commence following completion of the simulation training (if applicable), whereas they can commence immediately following study approval for the 'Expert' group. The surgeon-specific outcome measures will be the objective motion-analysis metrics generated by validated and extensively used wireless sensors placed on the elbows of surgeons under their sterile gowns during the operation; and subjective assessments of surgical trainee performance using validated and reliable forms of structured human grading. Patient-specific outcome measures will be collected for a pre-determined number of patients who have undergone a primary elective THR by any of the surgeon participants in this study. All patient-specific outcome measures (with the exception of a post-operative questionnaire) are routinely collected as part of the patients NHS clinical care, and no other additional investigations are required for conducting this research. All patients will be asked to provide their written informed consent for the use of their data in this study. The patient-specific outcome measures include: pre- and post-operative blood tests and radiograph (X-ray) analysis; the incidence of blood transfusions and any other peri-operative complications; the in-patient length of stay; and two patient-reported outcome measure (PROMs) questionnaires.

Statistical analysis will then be performed on the data collected, specifically aiming to identify any significant differences in either surgeon performance metrics, or patient outcome measures between:

- 1) The StR's who have undertaken additional simulation training versus those who have routine Deanery training.
- 2) The 'Trainee' group and the 'Expert' group. A sub-group analysis may be performed within the 'Expert' group also to determine any differences between the Consultants and Fellows.

In summary, this novel research will use validated methodology and routinely collected patient outcome measures in order to determine the impact of simulation training on surgical trainee performance and patient outcomes following a primary elective THR, and also help to benchmark an expert level of performance in this commonly performed and highly effective operation. The results of this study will hopefully help in shaping the future of orthopaedic surgical training and assessment within the United Kingdom.

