9.3. Subsequent Visits

Group 1a ('StR's') - Intervention group:

StR's randomised to the 'intervention group' will be required to complete the 4-week period of additional training outlined in section 9.3. Following completion of this additional training, participants within this group will undertake approximately 2 intra-operative assessments every 6 weeks over the duration of their 6-month clinical placements (total 8 assessments). The StR's will also undertake a final Technical Skills assessment in OOSEC Laboratory at 3 months into their placement (See Appendix A for Study Flow Diagram).

Group 1b ('StR's') – control group:

Participants within this group will undertake approximately 2 intra-operative assessments every 6 weeks over the duration of their 6-month clinical placements (total 8 assessments). The StR's will also undertake a final Technical Skills assessment in OOSEC Laboratory at 3 months into their placement (See Appendix A for Study Flow Diagram).

Group 2: 'Experts' and 'Fellows':

Following enrolment for participation in this study, all participants within this group will undergo a baseline practical skills assessment within the OOSEC. Participants within this group will then undertake a minimum of 5 separate intra-operative assessments each.

Patients:

Following enrolment for participation in this study, all patients will be asked to complete the pre-operative PROMs questionnaires (EQ-5D and OHS). These are part of routine clinical care, and are a mandatory for all patients undergoing THR in the NHS. The patients will not be asked to undertake any further assessments outside of their routine clinical care until the time of their scheduled post-operative out-patient department (OPD) clinic review appointment. All patients will only be followed up routinely following discharge by their named Consultant in an OPD clinic. This OPD appointment normally takes place 6 to 8 weeks following discharge. No additional clinic appointments or investigations will be required outside of the patients expected routine clinical care. At this visit the patients will be asked to complete the post-operative validated PROMs questionnaires (EQ-5D and OHS). This takes a few minutes and is the only extra outcome measure the patients are asked to complete.

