- 2b): Good overall with minor imperfections on femoral side.
- 3: Moderate concerns but does not require revision surgery.
- 4: Significant concerns requiring revision surgery.

Every patients post-operative x-ray will also be reviewed by the PI ([name]) for acetabular component positioning (inclination and version) using the methodology described by Bachhal [4]. This continuous data will be assessed for normality of distribution, and analysed using similar methodology as described above for the motion data. We will be looking for any statistically significant differences between the 2 groups of participants, within the two sub-groups of StR's (control and intervention), and also within the intervention sub-group in order to compare performance before and after additional training.

Other outcomes data:

Following collection of the outcome measures listed below, the normality of the data distribution will be checked with the Shapiro-Wilk test. Descriptive statistics will be used to outline the central tendency and variation of these data sets. Statistical analyses between each group of participants will be performed using either the parametric unpaired t-test or a non-parametric Mann-Whitney U test depending on the distribution of the data. Subsequent analysis of the outcomes data using a paired t-test, or Mann-Whitney U test will also be performed within the two sub-groups of the StR's (control and intervention), and also within the intervention sub-group in order to compare outcomes before and after additional training.

- Theatre time usage.
- Blood loss (pre-/post-op haemoglobin levels)
- In-patient length of stay.
- PROMs: EQ-5D and OHS.

The Chi-squared test (or Fishers exact test if the sample is <5) will be used to determine any significant differences between the groups regarding the incidence of blood transfusions or peri-operative morbidity.

All of these tests will be performed using the SPSS statistical package, which is available for any registered student on the University of Oxford current Licencing agreement.

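### The before/after-training test is planned in the trained arm only, and its only scheduled pre-training data are laboratory scores that both arms provide but no analysis names

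*Combined protocol and SAP*

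**What the plan says.** Section 11 (Analysis of motion data) plans two Mann-Whitney comparisons among the registrars (StRs). The first is randomised: it will "compare performance metrics between the two sub-groups of StR's (control and intervention". The second is "also within the intervention sub-group in order to compare performance before and after training".

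The second comparison recurs later in section 11. For cup inclination and version it is "also within the intervention sub-group in order to compare performance before and after additional training". For theatre time, haemoglobin, length of stay and PROMs the text reads "within the two sub-groups of the StR's (control and intervention), and also within the intervention sub-group in order to compare outcomes before and after" the additional training. The x-ray rating paragraph gives registrars before and after training as an example of an intra-group comparison. No comparison of change between arms is stated.

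On what is measured before training:

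- Section 9.2: "Following randomisation all StR participants will undergo a baseline written and practical skills assessment within the OOSEC".
- Section 9.6: "All participants within group 1 (StR's) will be asked to attend and complete baseline and final assessments within the OOSEC"; these consist of a multiple-choice questionnaire and a simulated procedure.
- Section 9.3, in the same words for Groups 1a and 1b: "The StR's will also undertake a final Technical Skills assessment in OOSEC Laboratory at 3 months into their placement".
- Section 2, on the surgeon and patient outcomes: "These outcome measures for the 'Trainee' group will commence following completion of the simulation training (if applicable"). Section 7 starts registrars' theatre assessments 6 weeks into the placement.

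The outcome table in section 6 lists neither the questionnaire nor the simulated procedure, and section 11 does not mention them.

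**The concern.** A trained registrar's change from baseline to 3 months has several sources: any effect of the package, routine Deanery training and operating on the placement, and familiarity from sitting the same kind of assessment twice. A p-value for that change in the trained arm alone cannot separate them. The control registrars continue routine training and sit the same two assessments, so their change measures everything except the package. A test that leaves them out gives up the protection that randomisation provides.

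At stake is the reading of a secondary but attractive result. A significant improvement after training could be reported even if the package taught nothing, while the data that would show this sit in the same dataset with no stated analysis. For the outcomes measured only in theatre or on patients, the problem is different: the schedule provides nothing to serve as the before value.

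**Working it through.** **1. Which outcomes have a pre-training value?**

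| Outcome | First measured in registrars | Pre-training value? |
|---|---|---|
| Theatre motion metrics, rating scales | After training; week 6 of placement (sections 2, 7) | No |
| X-ray rating, cup position, patient outcomes | Operations after training (section 2) | No |
| OOSEC questionnaire and simulated procedure | Baseline, both arms (sections 9.2, 9.6) | Yes |

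Pre-operative x-rays, haemoglobin and PROMs precede a patient's surgery, not the surgeon's training, so they do not fill the gap.

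**2. The plan's own figures.** The only sample-size arithmetic is the patient head count in section 3: 16 × 8 + 8 × 5 + 5 × 5 = 128 + 40 + 25 = 193, which reproduces. The documents give no alpha, power, SD, effect size or learning gain. The remaining steps therefore rest on assumptions.

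**3. What each contrast estimates.** Let L be the gain common to both arms and T the training effect.

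- Trained arm, after minus before: L + T.
- Control arm, after minus before: L.
- Difference in change between arms: (L + T) − L = T.

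With T = 0 the within-arm change still averages L. This holds whatever the size of L.

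**4. False-positive rates with T = 0.** Inputs: 6 to 8 registrars per arm (section 9.4). Assumed: two-sided alpha 0.05, bivariate normal before/after scores with SD 1, correlation 0.3 to 0.7, and L as shown. There were 20,000 simulated trials per setting (4,000 for ANCOVA). Ranges run over the correlation.

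| Gain L (SD) | Mann-Whitney, trained arm, n=8 | Signed-rank, trained arm, n=8 | Mann-Whitney, n=6 | Signed-rank, n=6 |
|---|---|---|---|---|
| 0.5 | 7–12% | 14–29% | 4–8% | 9–17% |
| 0.8 | 26–28% | 32–64% | 14–18% | 18–38% |
| 1.0 | 44% | 47–83% | 26–28% | 26–54% |

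At L = 0.25 SD and n = 8 the Mann-Whitney rejects in 1.5–4.3% of trials. It is conservative because it treats paired scores as independent. The signed-rank test there rejects in 7.6% (correlation 0.5) and 10.1% (correlation 0.7).

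*Hand check.* The paired t-test has noncentrality L√n / √(2(1−ρ)). For n = 8, L = 0.8, ρ = 0.5 this is 0.8 × 2.83 / 1 = 2.26. Against a critical value of 2.36 on 7 degrees of freedom, that implies rejection in about 50% of trials. The exact signed-rank test, which is coarser, gave 43%.

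**5. Contrasts that use the control arm, same settings, T = 0.**

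| Between-arm test | n=8 | n=6 |
|---|---|---|
| Mann-Whitney on change | 4.8–5.2% | 3.9–4.3% |
| ANCOVA on baseline | 4.2–5.7% | 4.6–5.3% |

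A between-arm Mann-Whitney on final scores alone gives 4.7–5.3% at n = 8.

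**6. Power of those contrasts for an assumed T = 1 SD.** At n = 8: change scores 34–65%, ANCOVA 46–70%, final scores alone about 44%.

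**The case against.** The strongest reply is that the sentence containing the before/after test first plans the randomised control-versus-intervention comparison. The before/after test is an addition, and no text says that it will be read as the training effect. This stands. A reader might infer that the trial has lost its controlled comparison; the documents do not support that, and common learning does not bias the planned contrast.

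Second, the link to the OOSEC scores is an inference. The sentence sits under motion data, and nothing says that sensors are worn in the laboratory. If performance metrics were meant to include OOSEC results, the same sentence would already compare them between arms, and only the use of baseline would be missing. So it goes too far to say that the control scores are certainly unused, or that the trial forfeits its only test of whether the package taught the skill. What stands is that the text leaves this open. If the OOSEC reading is rejected, the before/after test has no before data at all, and section 11 still needs correcting.

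Third, the paragraph on other outcomes speaks of analyses within both registrar sub-groups, which could include a within-control analysis. That is possible, but the before/after phrase is attached only to the intervention sub-group, and those outcomes have no pre-training values in either arm.

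Fourth, the gains are assumed, the scores are simulated as normal although section 11 expects non-normal motion data, and the highest rates come from a paired test that section 11 does not assign to this motion comparison. All true; the percentages illustrate and do not predict.

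Finally, a reader might infer a fixed interval of about two months between the end of training and the final assessment. The documents do not fix it: the course lasts 4 weeks in sections 2, 9.3 and 9.6 but 4 to 6 weeks in section 7, its start is not tied to placement entry in the text, and the Appendix A flow chart is not visible. The argument does not need the exact interval.

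**Conclusion.** The concern holds in a limited form and should be corrected, but it does not undermine the randomised comparison. A before/after test confined to the trained arm attributes the whole common gain to training. For OOSEC scores that is a bias of L, whose size the documents do not allow one to state. Under assumed gains of 0.5 to 1.0 SD, false positives at 8 per arm run from about 7 to 44% with the named Mann-Whitney and about 14 to 83% with a signed-rank test. At 0.25 SD or less the Mann-Whitney shows no inflation, though the estimated change is still biased.

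For theatre motion metrics, x-ray rating, cup position and the other patient outcomes, the before/after tests cannot be carried out on the visible schedule. This rests on the text of sections 2 and 7, since the flow chart could not be read.

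**What to change.** In section 11:

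- Replace the before/after test in the intervention sub-group with a between-arm comparison of the 3-month OOSEC questionnaire and simulated-procedure scores, one value per registrar, adjusted for the OOSEC baseline. In the simulations, adjustment gave more power than change scores at every correlation tried.
- Report within-arm changes for both arms descriptively, without p-values.
- Delete the before/after tests for x-ray rating, cup position and the other patient outcomes.
- State whether motion sensors are worn during the simulated procedure.

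In section 6, list the OOSEC scores as a secondary outcome.

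The baseline needs care. Section 9.2 places it after randomisation, and section 9.5 says registrars cannot be blinded, so effort at baseline could depend on allocation; the error rates for the baseline-adjusted contrasts assume that it does not. Take the baseline before the envelope is opened where possible. Otherwise, also report the unadjusted 3-month comparison, which does not use the baseline.

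The cost is wording in sections 6 and 11 and, where possible, a change of order within visit 1. No new data, visits or staff are needed. The downside is precision: a contrast of 8 v 8, or 6 v 6, has a wide interval, and even for an assumed effect of 1 SD the adjusted analysis at 8 per arm has only 46–70% power.
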